the primary owners of a mobile phone with text messaging service, which is anticipated to be at least 75% of parents in this population based on previous research on urban, low-income parents.^{59, 60}

Exclusion criteria: Parents of children with significant medical co-morbidities (e.g., sickle cell disease, insulin-dependent diabetes mellitus) will be excluded because of their increased interaction with healthcare providers.

Recruitment and Randomization

CRA's will identify potentially eligible patients through electronic admission board and medical record diagnostic codes after intake into the ED, and they will describe the study to potentially eligible parents while they are waiting to be seen by a provider. Interested families will be screened for eligibility. If eligible, parents will complete the consent process. (See section 5.2.a for more details.) Then the CRA will administer a baseline questionnaire focusing on health care utilization, asthma self-management and morbidity, parental self-efficacy and outcome expectations. After the questionnaire is completed, participants will be randomized to usual care or the intervention group (T2B). Randomization will occur automatically via the RedCap database system. Time allowing, participants randomized to the intervention will receive brief education on the 3 S's and orientation to the text message component (including an "opt-in" code) while in the ED or if necessary by phone within 48 hours. The text message education component will begin within 1 week after participants are randomized, allowing time for participants to enter the opt-in code.

Retention and Compensation

Parents will receive total compensation of \$110 for participation in the study to be dispensed as: \$20 gift card will be given to the parent after he/she completes the baseline interview and \$30 gift cards will be sent after the 3, 6, 12 follow-up interviews; Based on previous studies conducted by our research team with similar populations, this amount should be sufficient to compensate participants for their time and offset the cost incurred for the text messages (if any), but it will not be coercive, minimizing participation solely based on financial gain.

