Trained CRAs will conduct structured in-person interviews after participants have consented and before randomization. Follow-up interviews, lasting approximately 30 minutes, will be conducted by a trained CRA blinded to participants' randomization. In cases when no blinded CRA is available an unblinded CRA may complete the survey. Unblinded status will be documented for each survey conducted. Electronic medical record review will be conducted by trained study staff at the site where the participant was enrolled. Measures of asthma outcomes for this study are aligned with the recent recommendations of the Asthma Outcomes Groups for standardization of definitions and data collection methodologies for asthma research studies and clinical trials.^{75,76} All, but one of the following measures will be administered at each wave of data collection. The Asthma Self-Management Questionnaire will be administered at baseline and 12 months. (see appendix for Baseline Survey).

Distal Outcome Measures – Child Asthma Outcomes

ED visits for asthma care: Parents will report whether and how many times their child was taken to the emergency room because of asthma during the past 12 months using 2 questions administered in several national-scale surveys;⁷⁵ they will also indicate whether those visits included receipt of systemic corticosteroids.⁷⁶ We will validate a large portion of this data with EMR review because Seattle Children's is the primary ED utilized by young patients in the Seattle area and Mary Bridge Children's the primary ED utilized by young patients in the Tacoma area.

Asthma Morbidity: Asthma morbidity will be assessed by the questions used in the Inner City Asthma Consortium (ICAC)^{73, 74, 77, 78} and applied subsequently in numerous studies, including the study validating the IMPACT DC intervention.¹⁵ Morbidity will be measured as the number of days (or nights) of impairment in the prior 2 weeks.

Proximal Outcome Measures – Adherence to Treatment Recommendations

Primary Care Utilization: To maintain continuity in outcomes with the IMPACT DC RCT,¹⁵ we will ask parents to identify their child’s primary asthma health care provider, as well as their child’s primary care provider. A computed variable will indicate whether the named PCP is the child’s primary asthma health care provider. In addition, we will ask parents about frequency of PCP visits for asthma care at each telephone follow-up interview.

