COVER PAGE

Text2Breathe: Enhance Parent Communication to Reduce Pediatric Asthma Disparities (T2B)

NCT03032159

July 10, 2014

C.5. Statistical Analyses

C.5.a: Preliminary Descriptive Analysis of Data

We will summarize all baseline variables overall and by study arm to assess the balance achieved by randomization and to check assumptions such as normality and equality of variances. The distributions of continuous variables will be summarized using means, standard deviations, medians, and ranges. Categorical variables will be summarized using frequency distributions. Non-parametric tests (e.g., Wilcoxon rank-sum and Fisher's exact) will be used in subsequent analyses as needed. Cronbach alpha reliabilities will be estimated for 12 all standardized instruments to assess whether the instruments are as reliable in our target population as in the population on which the instruments were validated. Frequency of missing data for each outcome variable will be determined at each time point. Baseline characteristics of missing and non-missing respondents at the 3, 6, 12 and 24 month time points will be compared to assess for attrition bias. We will employ multiple imputation to account for missing data, if necessary.^{84, 85} We will examine counts of mobile interactions captured by Rip Road (e.g., number of messages received and sent by each participant; See section 5.1.d.) to assess engagement with the intervention, overall and by participant characteristics.

C.5.b: Analysis Plan for Addressing Specific Aims

In **Aim 1**, to assess the intervention effect on the primary and secondary distal outcomes (i.e., the number of ED visits for asthma care during the 12-month interval following randomization, and the number of days of impairment during the two weeks prior to the 12-month interview, respectively), we will utilize negative binomial regression, a generalization of Poisson regression which yields unbiased inference even if the outcome variable is over-dispersed (i.e., the variance exceeds the mean) to estimate incidence rate ratios (IRRs) and 95% confidence intervals (CIs) for count data. The single independent variable in each model will be study group, and the exponentiated form of its regression coefficient will reflect the relative difference between groups in the annual rate of ED visits or frequency of impaired days.

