In **Aim 2**, we will implement a negative binomial regression model to estimate the IRR and 95% CI for number of follow-up visits with the PCP for asthma care over 12 months in the intervention group compared to the usual care group. In addition to the group variable, the model will include a covariate to account for PCP visit frequency prior to randomization. The exponentiated form of the coefficient of the group term will reflect the relative difference between groups in annual rate of PCP follow-up visits for asthma care. We will use linear regression models to examine the intervention effect on knowledge of self-management (continuous scale score). The model independent variables will include study group and pre-randomization level of knowledge of self-management. The magnitude of the group coefficient will provide an estimate of the size and direction of difference between groups controlling for differences in pre-randomization levels.

We will also assess whether primary care utilization (annual rate of follow-up visits) and increased knowledge of self-management mediate the relationship between the assigned communication intervention and child asthma outcomes (defined as frequency of ED and urgent care visits for asthma care and days of impairment). To do so, we will use path analysis models at baseline and each follow-up time separately. To test these hypotheses using longitudinal data, growth trajectories of each outcome will be modeled using multi-process latent growth models (LGM) of these

proximal and distal outcomes. The hypothesized mediating effects of the proximal outcomes will be tested by relating the intervention condition, the latent slope growth factors of the multiple growth processes, and the distal outcomes.⁸⁶

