In **Aim 3**, we will use linear regression models, as above, to evaluate the intervention effect on measures of self-efficacy and outcome expectations. We will then use path analysis to assess whether parental self-efficacy and outcome expectations (defined using the three validated instruments) mediate intervention effects on PCP follow-up rates and knowledge of self-management. Although the data collected at the 12-month time point will be used as our primary indicator of intervention effectiveness, we will also utilize data collected through the full 24-month follow-up period to evaluate sustainability of the hypothesized effects of the intervention in the same series of analyses. The above analyses estimate the impact of the intervention at observed levels of acceptance of the intervention and thus estimate the expected average effectiveness of the intervention if implemented in a similar population. We will also estimate the magnitude of the effect on each outcome under alternative levels of engagement in the intervention to provide a range of estimated effects based on greater and lesser levels of engagement. Moreover, we will examine potential moderating effects of race/ethnicity on the intervention effects.

C.5.c: Sample Size Estimate

All sample size and power analyses are based on a 2-tailed type 1 error of 5% in final analyses based on 12 month follow-up results. For the primary outcome under **Aim 1** (number of ED visits for asthma care during a 12-month interval), we calculated that a sample size of 125 per study group provides at least 90% power to detect a clinically important 35% reduction in the T2B group compared to the estimated average rate of 1.28 ED visits per year in the usual care group (based on 2012 ED records). For the primary outcome under **Aim 2** (number of PCP visits for asthma care during a 12-month interval), we calculated that a sample size of 120 participants per group provides 90% power to detect an increase to the recommended 3 annual visits in the T2B group over the observed rate of 1.8/year in the previous IMPACT DC sample.⁷ For the other outcomes under Aim 3 (self-efficacy and outcome expectation), a sample size of 85 per group provides 90% power to detect a 0.5 SD effect size difference between study groups. A feasible **analytic sample size of 110** ensures >80% power in all aforementioned analyses.

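### The primary ED-visit model leaves out the 12-month ED-visit count collected before randomisation; the test is valid, but some efficiency may be lost

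*SAP*

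**What the plan says.** SAP C.5.b, Aim 1, analyses ED visits in the 12 months after randomisation, and impaired days in the two weeks before the 12-month interview, by negative binomial regression. On covariates it says: "The single independent variable in each model will be study group".

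The baseline ED-visit count is available. Under Recruitment and Randomization, the protocol has staff "administer a baseline questionnaire focusing on health care utilization" among other topics, and randomisation follows its completion. Under Distal Outcome Measures, the ED item asks "how many times their child was taken to the emergency room because of asthma during the past 12 months". Under Data Collection, "All, but one of the following measures will be administered at each wave of data collection"; the exception is the Asthma Self-Management Questionnaire, not the ED item.

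For Aim 2, the SAP uses the same model type for 12-month PCP visits, but there "the model will include a covariate to account for PCP visit frequency prior to randomization". The linear model for self-management knowledge also includes its baseline score. No reason is given for treating the primary outcome differently.

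**The concern.** A child's previous ED use would be expected to predict later ED use. If it does, leaving it out of the model gives a less precise estimate than the collected data allow. This is the trial's primary outcome, and its planned power depends on a dispersion that the SAP does not state.

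There is also a prespecification point. SAP C.5.a will examine baseline balance, but Aim 1 has no rule for what follows if prior ED use differs between arms. In the team's preceding face-to-face trial, described in the protocol background, variables that differed at baseline were controlled in the analysis. Naming the covariate now avoids a choice made after the data are seen.

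**Working it through.** **Inputs.** From SAP C.5.c: two-sided 5% test; control rate 1.28 ED visits per year; 35% reduction, so 1.28 × 0.65 = 0.832; 125 per group for at least 90% power; analytic sample 110, taken as per group since 110/0.8 = 138 per group; PCP visits 1.8 versus 3 per year with 120 per group for 90% power. Not in the documents, so assumed: dispersion k, baseline mean (1.28) and frailty correlation (0.3 to 0.9).

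**Step 1: the SAP's own figures.** The sizing method is not stated. I assume a Wald test on the log rate ratio, with variance (1/m0 + 1/m1 + 2k)/n.

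- ED visits: 1/1.28 + 1/0.832 = 1.983 and ln(0.65)² = 0.1856. The 90% requirement at k = 0 is 10.507 × 1.983/0.1856 = 112.3, so 113 per group; power at 125 is then 92.8%.
- The statement that "a sample size of 125 per study group provides at least 90% power" holds for k up to (125 × 0.1856/10.507 − 1.983)/2 = 0.112.
- Power of 80% at 110 per group holds for k up to (110 × 0.1856/7.849 − 1.983)/2 = 0.309.
- PCP visits: 1/1.8 + 1/3 = 0.889 and ln(3/1.8)² = 0.2609. The statement that "a sample size of 120 participants per group provides 90% power to detect an increase to the recommended 3 annual visits" corresponds to k = (120 × 0.2609/10.507 − 0.889)/2 = 1.05.
- If ED visits had that second k, Aim 1 power would be 66.5% at 125 per group and 61.0% at 110.

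On this formula the two sizing statements imply very different dispersion for two 12-month visit counts.

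**Step 2: what adjustment gains.** Simulation with gamma frailties correlated between baseline and follow-up (Gaussian copula), maximum-likelihood negative binomial fits with and without log(baseline visits + 1), 110 per group, 3,000 replicates per cell. Entries are for frailty correlation 0.3 / 0.6 / 0.9. Simulation error on power is about 1 point or less.

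| k | Variance ratio, adjusted/unadjusted (model-based) | Power %, unadjusted → adjusted |
|---|---|---|
| 0.112 | 1.000 / 0.998 / 0.992 | 86.6→86.6 / 87.0→87.0 / 87.9→88.2 |
| 0.309 | 0.995 / 0.978 / 0.950 | 80.7→80.6 / 81.0→82.3 / 81.3→83.1 |
| 0.5 | 0.990 / 0.959 / 0.903 | 75.5→75.8 / 75.0→77.3 / 74.7→79.0 |
| 1.05 | 0.981 / 0.917 / 0.791 | 61.0→62.0 / 61.3→65.0 / 62.2→72.9 |

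The correlation between baseline and follow-up log(count + 1) in these four rows runs 0.03-0.09, 0.07-0.22, 0.10-0.30 and 0.15-0.45. Empirical variance ratios show the same pattern: 0.992 at k = 0.112 and 0.815 at k = 1.05, both at frailty correlation 0.9.

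**Step 3: every child has at least one baseline visit.** Children are enrolled during an ED visit for asthma, so this applies if that visit is counted. The follow-up control mean stays at 1.28. The entries for correlations 0.3 and 0.6 use 1,500 replicates.

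| k | Variance ratio, correlation 0.3 / 0.6 / 0.9 | Power change, points |
|---|---|---|
| 0.112 | 1.000 / 0.998 / 0.995 | −0.1 / +0.1 / −0.1 |
| 0.309 | 0.997 / 0.987 / 0.968 | −0.3 / +0.7 / +0.4 |
| 0.5 | 0.994 / 0.974 / 0.940 | −0.4 / +1.8 / +2.8 |
| 1.05 | 0.989 / 0.953 / 0.876 | −0.2 / +2.2 / +5.3 |

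**Step 4: validity and robustness.**

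- With no true effect (4,000 replicates, correlation 0.9), rejection rates without and with the covariate are 5.4% and 5.6% at k = 0.112, 4.8% and 4.8% at k = 0.309, and 5.9% and 5.9% at k = 1.05. The covariate does not affect type I error.
- The mean log rate ratio is unchanged to within 0.002.
- Using the raw count as covariate gives variance ratios of 0.993, 0.952, 0.912 and 0.829 at correlation 0.9, so the conclusion does not rest on the log form.
- Log-normal frailties (600 replicates) give about 0.99 at k = 0.112, 0.97 to 0.89 at k = 0.5 and 0.98 to 0.71 at k = 1.0, for correlations 0.5 to 1.0.

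**The case against.** The strongest reply is that this is a preference. The Aim 1 model is explicit, prespecified and valid, and nothing requires the aims to share covariates. On the SAP's own Aim 1 sizing the gain is nil. Even at k = 0.309, the most that still gives 80% power at 110 per group, the power changes in the first table are −0.1 to +1.8 points, close to simulation error.

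The larger gains need a k borrowed from PCP visits. Nothing links that dispersion to ED visits, and because the Aim 2 model is baseline-adjusted, the k behind its sizing may be a residual one. If k really were 1.05, even the best adjusted power (72.9%) would fall short of 80%. Parent recall over 12 months is also imperfect, which would shrink the gain, and counting the enrolling visit shrinks it further.

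All of this stands as a limit on size. It does not remove the point: the documents do not establish that k is low, the covariate costs almost nothing when k is low, and it helps most where the primary analysis would be weakest. Baseline data may enter the SAP's path and growth models, but those are not the primary test.

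Adjusting ED visits and not impaired days would make the two Aim 1 models differ. That is accepted, because no gain has been established for impaired days.

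**Conclusion.** The point holds as a recommended improvement, not as an error or contradiction. The primary ED-visit analysis omits a prognostic count that is collected before randomisation, while the Aim 2 visit-count model uses its own. The group-only estimate is not biased by this and its test is valid.

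The loss is negligible (0-1% of variance) at k = 0.112, where the Aim 1 sizing sits. It is material only if dispersion is near the Aim 2 value and the correlation is high: up to 21% of variance and 10.7 power points, or about 12% and 5.3 points if every child has at least one baseline visit. At a moderate frailty correlation of 0.6 and k = 1.05, the gain is 3.7 points, or 2.2 with at least one baseline visit.

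These figures rest on the assumed sizing formula, baseline mean, frailty model and correlations, and on baseline counts recalled without error. Confidence in the size is therefore only moderate. The finding covers ED visits only.

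**What to change.** Amend the Aim 1 text in SAP C.5.b for the primary outcome only, for example:

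> The primary ED-visit model will include study group and log(baseline 12-month ED visits + 1), with the enrolling visit counted in the same way for every child. The unadjusted model will be reported as a sensitivity analysis.

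Keep the group-only model for impaired days; a baseline-adjusted version may be reported as supportive.

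The cost is SAP wording, one degree of freedom and one counting rule for the enrolling visit. No new data are needed. The change must be made before outcome data are examined by group. If k is as low as the Aim 1 sizing implies, the benefit will be close to nil.

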enhanced HC intervention to parents of children with other chronic conditions. In addition, the expedience of scaling up a text-message protocol means that our intervention can easily be adapted to reach a broader audience in a cost-effective manner when compared to ongoing face-to-face interventions. If efficacy is demonstrated, another next step will be to expand the program to other healthcare settings, such as primary care practices.

Study Design

We propose to conduct a RCT with low-income parents of children with physician-diagnosed asthma, ages 2-12 years inclusive, who are seen in the Seattle Children's or Mary Bridge Children's ED [for asthma care] to test the efficacy of our mHealth HC intervention, T2B, primarily for reducing ED/urgent care visits for asthma care. Each hypothesis will be tested by contrasting parents receiving T2B with parents receiving only standard ED-based care for their child's asthma, over 12 months.

Study Schedule

Data on child and parent outcomes will be collected in-person at enrollment and by telephone interviews at 3, 6, and 12 months post-enrollment. These telephone interviews will all be coordinated and conducted by the Seattle Children's study staff. Given the highly seasonal nature of asthma-related morbidity, the text message component of the intervention will continue for 12 months (3 months of biweekly educational interactive text messages; ongoing parent-initiated access to key messages and reminder text messages for PCP follow-up/medication refills/annual flu vaccines) allowing for the capture of individual variability in disease course. (Figure 3).

[figure not shown]

Figure 3

Study Population

The study population will be parents/guardians of Medicaid- insured patients seen in the Seattle Children’s or Mary Bridge Children’s ED for treatment of their asthma. These are patients whose asthma is not yet well controlled and who experience the greatest morbidity due to environmental and social factors and are thus the most resource-intensive group.

Inclusion criteria: Parents of Medicaid-insured children age 2 to 12 years inclusive with physician- diagnosed asthma for at least 12 months will be eligible. Older children/adolescents are excluded because they assume greater responsibility for asthma self-management, and their communication with providers becomes more independent over time. Parents must be

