To assist with subject retention, considering the transient nature of this community and the fact that phone numbers are frequently disconnected and/or changed, we will obtain up to 3 contacts' phone numbers from each participant at enrollment, and review and update contacts at each follow-up interview. Using this method in previous studies, our research team has successfully maintained 90% subject retention at 6-month follow-up.¹⁵ In addition, Rip Road has extensive experience working with underserved populations [through public health departments] and pay-as-you-go service providers, and can thus nimbly respond and adapt to

any service interruptions. The window for follow up visits will be two weeks prior and post the due date for the 3 and 6 month follow up time points and 1 month prior and post the due date for 12month follow up time point. To enhance our ability to retain participants for, at each wave of follow-up, the system will send text message reminders to participants to alert them that their follow-up call is approaching and to contact the study coordinator to schedule. If a call has not already been scheduled as of day 1 of the open window, a CRA will contact the family. If no contact has been made as of the due date an online version of the follow up survey will be emailed to the provided email contact. If the participant misses a wave they will still be called for the next follow-up. Information for alternative contacts will also be collected at the time of consent. These contacts will be utilized when participants' provided phone numbers are inactive.

Data Collection

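### Read as written, the H2c path and growth models use a 12-month ED look-back that is 75% pre-randomisation at month 3 and 50% at month 6, so early effects are diluted and their timing distorted

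*SAP*

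**What the plan says.** The Protocol (Data Collection, Distal Outcome Measures) measures ED use by asking parents "how many times their child was taken to the emergency room because of asthma during the past 12 months". The same section states: "All, but one of the following measures will be administered at each wave of data collection". It then names the exception: "The Asthma Self-Management Questionnaire will be administered at baseline and 12 months". The ED item is therefore repeated at every wave, and Study Schedule places the follow-up waves "by telephone interviews at 3, 6, and 12 months post-enrollment". Electronic record review is planned to validate a large part of the parent report.

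SAP C.5.b, Aim 2, takes the frequency of ED and urgent care visits as one of the distal outcomes in the H2c mediation analysis. It says "we will use path analysis models at baseline and each follow-up time separately", and that "growth trajectories of each outcome will be modeled using multi-process latent growth models (LGM"). Mediation is then tested through the latent slope factors. The section gives no count since the last interview, no exposure term, no exclusion of visits before randomisation and no rule for the enrolment visit. Only the Aim 1 outcome is tied explicitly to the 12 months after randomisation.

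**The concern.** A 12-month look-back fits a month-12 interview. At months 3 and 6 it reaches back to before the child entered the trial. T2B cannot have changed those visits, and PCP use after enrolment cannot have mediated them. Three things are at stake in H2c:

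- The month-3 and month-6 path models test a diluted effect that is partly out of temporal order.
- The growth model sees an effect that builds up as the window moves forward, even if the true effect is immediate and constant.
- Successive windows overlap, so the same visit is counted at more than one wave and adds serial correlation.

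The early waves matter here. The team's earlier trial of the face-to-face programme (Protocol, Validation of PEPAC) reported lower ED use at two months that was not sustained at six. A measure that hides early effects is poorly suited to testing how such effects arise.

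**Working it through.** **Inputs.** Control rate 1.28 ED visits per year, a 35% reduction (ratio 0.65, so T2B 1.28 × 0.65 = 0.832), two-sided 5%, 125 per group for at least 90% power, and an analytic sample of 110, read as per group (all SAP C.5.c). Waves at 0, 3, 6 and 12 months (Protocol, Study Schedule). Interview windows (Protocol, Retention and Compensation): "two weeks prior and post the due date for the 3 and 6 month follow up time points". For month 12 the allowance is one month either side.

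**Plan's own figure.** n per group = (z₀.₉₇₅ + z₀.₉₀)² × (1/m₀ + 1/m₁ + 2k) / (ln RR)². The SAP gives no dispersion k. With k = 0: 10.507 × (0.781 + 1.202) / 0.1856 = 112.3, so 113. At 125 per group the power is 92.8%, which is consistent with the stated minimum of 90%; exactly 90% would need k of about 0.11. This point does not dispute that calculation; it only borrows its rates.

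**Share of the window before randomisation**, (12 − t)/12:
- Month 3: 9/12 = 75% (70.8% to 79.2% across the interview window).
- Month 6: 6/12 = 50% (45.8% to 54.2%).
- Month 12: 0% (8.3% if the interview is at month 11).

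**Expected counts and ratios.** Assume the rate before enrolment equals 1.28, the true ratio is constant at 0.65, and interviews fall on the due date. T2B count = 1.28 × (12 − t)/12 + 0.832 × t/12. Counting the enrolment visit adds 1 to both arms at months 3 and 6.

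| Month | Control | T2B | Ratio | Ratio with enrolment visit |
|---|---|---|---|---|
| 3 | 1.28 | 1.168 | 0.91 | 2.168/2.28 = 0.95 |
| 6 | 1.28 | 1.056 | 0.83 | 2.056/2.28 = 0.90 |
| 12 | 1.28 | 0.832 | 0.65 | 0.65 |

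If the pre-enrolment rate is instead 2 to 4 per year (an assumed range), the ratios without the enrolment visit are 0.94 to 0.97 at month 3 and 0.86 to 0.92 at month 6.

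**Dilution expressed as power.** For a simple two-arm comparison of these counts at 110 per group, k = 0 and no enrolment visit, the same formula gives about 11%, 34% and 89% at months 3, 6 and 12. This is not the power of the mediation test.

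**Slopes.** Least squares over 0, 3, 6 and 12 months (mean 5.25, Sxx = 78.75). Without the enrolment visit the control arm is flat, and T2B runs 1.28, 1.168, 1.056, 0.832, a straight line of −0.448/12 = −0.037 per month. The true T2B rate after randomisation is flat at 0.832. The enrolment visit adds the sum of the time deviations at the waves where it is counted, divided by Sxx:

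| Enrolment visit counted at | Control slope | T2B slope | Difference | Share of T2B slope due to that visit |
|---|---|---|---|---|
| No wave | 0 | −0.037 | −0.037 | 0% |
| Months 3 and 6 | −1.5/78.75 = −0.019 | −0.056 | −0.037 | 34% |
| Baseline, 3 and 6 | −6.75/78.75 = −0.086 | −0.123 | −0.037 | 70% |

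**Overlap.** The baseline and month-3 windows share 9 of 12 months, as do those of months 3 and 6; those of months 6 and 12 share 6.

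**The case against.** **The variable is inferred.** C.5.b does not name the ED measure for H2c. Its outcome includes urgent care, while the Protocol item covers the emergency room only. No follow-up questionnaire is in the text, record review could supply dates, and the team's earlier trial reported ED visits between baseline and its two-month assessment. This stands as a limit: the sponsor may intend interval counts. It does not remove the point, because the repeated 12-month item is the only per-wave ED measure defined, and record review is described as validation and not as the source.

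**The common fall cancels between arms.** This stands. The enrolment visit adds equally to both arms, so the between-arm slope difference is −0.037 per month under every reading, and it comes from the assumed true effect. A reader might infer that the slope factor is merely an artefact, or that most of the T2B slope is. The documents do not support that. The 70% figure needs the enrolment visit counted at baseline as well as at months 3 and 6, yet the baseline questionnaire is given during that same ED attendance, so its inclusion there is uncertain.

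**Limited reach.** Month 12 is the primary indicator of effectiveness, and self-management knowledge, one of the two H2c mediators, is measured only at baseline and month 12. The damage to the month-3 and month-6 path models therefore concerns mediation through PCP visits. This also stands, and it keeps the point within a secondary hypothesis.

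**Conclusion.** The concern holds for the H2c path and growth models. Followed as written, the plan gives diluted ED ratios of about 0.91 and 0.83 at months 3 and 6 for a true 0.65 (0.95 and 0.90 with the enrolment visit), and turns an immediate, constant effect into a linear one. These sizes assume equal rates before and after enrolment, a constant true ratio and interviews on the due date. The 75% and 50% shares need only the last of these.

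Two stronger readings should be set aside. First, a spurious fall in the control arm is not inevitable: it appears only if the enrolment visit is counted or the pre-enrolment rate is above 1.28. Both are plausible, since children enrol at an ED visit, but neither is stated. Second, the Aim 1 primary result is not undermined: its outcome is defined after randomisation and the look-back fits at month 12, except that an interview up to a month early could reach the enrolment visit. The SAP should be corrected before H2c is analysed.

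**What to change.** For the H2c path and growth models, define ED visits at each wave as visits after randomisation in the non-overlapping interval since the previous scheduled wave: 0–3, 3–6 and 6–12 months, and likewise for any later wave used. Exclude the enrolment visit and enter log interval length as the exposure. Obtain the counts by anchoring the follow-up item to the last interview (or to enrolment, taking differences), supported by dated record visits where available. Records cover only part of the visits, so they cannot replace the parent report. Do not use the month-3 and month-6 answers to the 12-month item as outcomes. Keep the 12-month count for Aim 1. Whether the baseline 12-month count becomes a covariate or the first growth point is a modelling choice that the SAP should state. If interval counts were already intended, a short SAP statement of this definition settles the matter.

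The cost is SAP wording and a changed recall anchor, with no extra patients or visits. The drawback is smaller, noisier counts: in months 0–3 about 1.28 × 3/12 = 0.32 against 0.832 × 3/12 = 0.21.
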